### 3.3 Medical History

Any condition entered on the *relevant medical history / current medical conditions* CRF will be coded using the MedDRA dictionary. Frequency tables will be provided by primary system organ class, preferred term and treatment group.

Adverse events occurring between screening and baseline will also be reported as medical history, but additionally reported separately as adverse events occurring between screening and baseline.

#### **4 Study medication**

The duration of the double-blind treatment phase will be computed as the time from the first injection to the first out of

1. the last injection date plus a quarter year (91 days),
2. the patient's death
3. the patient's study completion visit during the study close-out period
4. or the analysis cut-off.

This algorithm reflects the planned treatment schedule and the long half-life of the study drug. Missing dates in this algorithm will be imputed in the same way as missing dates for time-to-event analyses.

The duration of the post-treatment phase will be computed as the number of days from the day after the end of the double-blind treatment phase to the end of the post-treatment phase. If the end of the double-blind treatment phase coincides with the end of the double-blind phase, then the duration of the post-treatment phase will be 0 days.

The duration of the double-blind phase and double-blind treatment phase will be summarized for the FAS and SAF by treatment group descriptively including by duration categories. Overall patient-years will also be displayed and will be computed as the sum of patient days for all patients divided by 365.25. The duration of treatment, and of exposure will be summarized for the SAF by treatment group descriptively including by duration categories. Overall patient-years of treatment will also be displayed and will be computed as the sum of patient days of treatment for all patients divided by 365.25.

Duration of exposure to study treatment excluding interruptions will be computed and summarized as above for the SAF, but not counting periods during which the last injection was more than a quarter year ago. Duration of exposure will also be summarized for patients who are alive at the end of the study.

An interruption is defined as the period of time in which IP is deemed to be inactive. In other words, if the date of the last dose + 91 days, falls prior to the following dosing date, then the difference between these is equivalent to the interruption duration. It should be noted that a single interruption may span multiple scheduled administrations of IP.

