Patients will have scheduled assessments at months 0.5, 1.5, and 3 after randomization and quarterly visits thereafter to evaluate safety and the occurrence of any trial endpoints, as well as, to receive scheduled (excluding month 1.5) subcutaneous injections of active therapy and/

or placebo.

The pivotal phase is event driven and designed to complete when a total of 1,400 patients have experienced a primary cardiovascular endpoint. Double blind treatment will be continued until the target number of primary cardiovascular endpoints has been reached. Sites will then be notified to have all patients return to complete an pivotal phase EOS visit. The elapsed calendar time to reach conclusion of the study is estimated to be approximately 6 years of treatment and follow-up from the start of enrollment in the trial to when 1,400 patients have had a confirmed adjudicated cardiovascular event.

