5.5.11 Early study termination

Novartis is committed to follow the IHC Harmonized Tripartite Guidelines for Good Clinical Practice (GCP) in implementation of this trial. The sponsor can terminate the study prior to completion of the trial in the case of a probable negative risk-benefit balance. Furthermore, the study can be terminated at any time for any reason by Novartis. Should this be necessary, patients should be seen as soon as possible and treated as described in [Section 6](#). The investigator may be informed of additional procedures to be followed in order to ensure that adequate consideration is given to the protection of the patient's interests. The investigator will be responsible for informing IRBs and/or ECs of the early termination of the trial.

6 Visit schedule and assessments

[Table 6-1](#) lists all of the assessments of the pivotal phase and indicates with an “x” when the visits are performed. Patients should be seen for all visits on the designated day or as close to it as possible. The study assessment schedule below outlines all procedures performed on patients at scheduled visits. The administration of study treatment is performed as per the visit assessment schedule at study sites by trained site staff after the completion of all other assessments.

[figure not shown]
The visit assessments listed below are for the estimated timeframe a patient would participate in the study. This is an event driven trial and will be stopped when the target number of primary cardiovascular endpoints have been accrued (please see [Section 9](#) for details). All patients will continue study treatments and visits until the event target has been reached. Patients who complete the 36 months will still be required to return to the clinic every 6

months for study assessments and quarterly for study treatment until notified by the site staff of pivotal phase completion. Only when the site staff has been notified of the pivotal phase completion by Novartis will the patients with a glycemic status of prediabetes from both randomization and pivotal phase EOS visit be asked to enter the 6-month study drug washout at their pivotal phase EOS visit.

Patients should attend visits, where labs are drawn, in a fasting state of 10 hours.

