9.3 Treatments (study drug, rescue medication, other concomitant therapies, compliance)

Study drug

The duration of the randomized treatment received during the double-blind pivotal phase will be computed as the time from the first injection to the first out of

1. the last injection date plus a quarter year (91 days),
2. the patient's death
3. or the patient's pivotal phase completion visit during the pivotal phase close-out period.

This algorithm reflects the planned treatment schedule and the long half-life of the study drug. The duration of the treatment period will be summarized for the full analysis set and safety set by trial part and treatment group descriptively including by duration categories. The overall patient-years of treatment will be computed as the sum of patient years of double-blind treatment for all patients.

Duration of exposure to study treatment excluding interruptions will be computed and summarized as above, but not counting periods during which the last injection was more than a quarter year ago.

Prior and concomitant therapies

Prior or concomitant medications will be summarized for the safety set and full analysis set in separate tabulations by trial part based on the coding dictionary used. Medications will be presented in alphabetical order, by preferred terms and grouped by anatomical main group. Tables will show the overall number and percent of patients receiving at least one drug of a particular preferred term and at least one drug in a particular anatomical main group.

Prior medications and significant non-drug therapies are defined as any medications and significant non-drug therapies taken prior to the randomization visit. Concomitant medications and significant non-drug therapies are defined as those used during the double-blind period. Concomitant medications that were prohibited as per protocol and given during the conduct of the study as well as significant non-drug therapies will be summarized.

Furthermore, the following classes of medications to be precisely defined in the statistical analysis plan, at time of randomization and during the double-blind period, which are relevant to program indication, will be summarized separately:

- Anti-ischemic agents
 - Beta blockers
 - Intravenous or oral nitrates
 - Calcium channel blockers

- Anti-platelet agents
 - Acetylsalicylic acid (aspirin)
 - Non-aspirin oral anti-platelet agents (like P2Y12 inhibitors clopidogrel and prasugrel)

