### **3 Patient disposition, background and demographic characteristics**

#### **3.1 Patient disposition**

The number of patients screened, randomized and included in the full analysis set (FAS), the per protocol set 1 (PPS1), and the safety set will be presented by treatment group and overall for the screened set, as well as by trial part. For the screened set the reasons for screen failures will be tabulated. The number and percentage of patients in the randomized set who completed the study, who discontinued the study (lost to follow-up, patient/guardian decision, technical problems, death), the reason for discontinuation of study medication, and vital status (known vs unknown for lost to follow-up and patient/guardian decision) will be presented for each treatment group and all patients, as well as by trial part. Some patients may have multiple visits where drug is not administered prior to permanent discontinuation. Each visit may have a different reason for not administering drug. For these cases, the following hierarchy will be used to assign the most conservative reason for permanent discontinuation of study medication:

- If a patient has at least one AE with an outcome/ action reported as permanent treatment discontinuation, then AE will be the reason
- If the scenario in bullet 1 did not occur and there is at least one reason on the Dosage Administration Record CRF that states the reason for not administering study medication is “ADVERSE EVENT”, then AE will be the reason
- If the scenarios in bullets 1 and 2 did not occur, the reason associated with the last visit the patient actually came into the clinic will be used as the reason for permanent discontinuation of study medication if the patient did not receive study medication at that last in-clinic visit. If the patient did receive study drug at the last in-clinic visit, the reason for not administering study drug associated with the first visit that the patient did not come into the clinic will be used as the reason for permanent discontinuation of study medication.

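### Does counting every day beyond 91 days after an injection as an interruption, with no tolerance, distort reported exposure enough to need a new rule?

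*SAP*

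**What the plan says.** SAP section 4 (Study medication) plans two related summaries. Treatment duration runs from the first injection to 91 days after the last one, or to death, the completion visit or the analysis cut-off if earlier. Exposure excluding interruptions is computed in the same way, "but not counting periods during which the last injection was more than a quarter year ago". An interruption is time during which the product is regarded as no longer acting, and the rule is that "if the date of the last dose + 91 days, falls prior to the following dosing date, then the difference between these is equivalent" to its length. Protocol 9.3 has the same cut-off: "not counting periods during which the last injection was more than a quarter year ago". Neither text allows any grace days.

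The dosing calendar is looser. Protocol 3.1 states: "Patients will have scheduled assessments at months 0.5, 1.5, and 3 after randomization and quarterly visits thereafter". Protocol section 6 gives no numeric window for pivotal-phase visits, only that "Patients should be seen for all visits on the designated day or as close to it as possible". Protocol 5.1 sets a minimum of 30 days between dosing visits after Visit 3 but no maximum, and it labels the first quarterly dose both week 12 and month 3.

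**The concern.** A quarter of a 365.25-day year is 91.3 days, so whole-day visit dates on a month-based schedule must include some 92-day gaps. Under the rule a patient who received every dose on the planned day still shows interruptions. The rule is also one-sided: days beyond 91 are deducted, and a short gap that follows does not restore them, so ordinary irregularity in visit dates accumulates.

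At stake is how well the table of exposure excluding interruptions reflects treatment actually missed. SAP section 7 describes this as the intended only pivotal trial and lists exposure among the key safety outputs to be repeated by subgroup. Two alternatives suggest themselves: count an interruption only when a dose was recorded as not given (SAP 3.1 refers to a "Dosage Administration Record CRF that states the reason for not administering study medication"), or only when the gap exceeds 119 days, the SAP's on-treatment limit.

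**Working it through.** **Inputs.** Coverage of 91 days per injection (SAP 4). Year of 365.25 days: SAP 4 has patient-years "computed as the sum of patient days for all patients divided by 365.25", and Table 2-4 uses 365.25/12 as the month. Doses at month 0, week 2, month 3 and quarterly thereafter (Protocol 5.1). On-treatment limit of 119 days (SAP 2.3.4). The documents give no figure for the spread of visit dates, so any such figure below is an assumption.

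**The plan's own figures.** 365.25 / 4 = 91.3125, which rounds to 91. 91 + 28 = 119. Both reproduce.

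**Rule.** Interruption days for one gap = max(0, gap − 91).

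**Perfect attendance, no dose missed, four years (1,461 days).** The gaps up to month 3 (14 and 77 days) cost nothing. Months 3 to 48 contain 15 quarterly gaps.

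- SAP month length: dose days 91, 183, 274, 365, 457, 548, 639, 730, 822, 913, 1004, 1096, 1187, 1278, 1370, 1461. Five of the 15 gaps are 92 days and ten are 91. Loss: 5 × 1 = 5 days; 5 / 1,461 = 0.34%.
- Same calendar day each quarter, over 1,461 consecutive start dates: 57.9% of gaps are 92 days. Mean loss: 0.579 × 15 = 8.7 days, 0.59%. Range: 7 to 12 days, 0.48% to 0.82%.
- Strict 13-week spacing: every gap is 91 days. Loss: 0.
- Week 12 taken literally as day 84, with month 6 at day 183: that gap is 99 days and costs 8 days once, in place of the 1 day counted above. Loss: 5 − 1 + 8 = 12 days; 12 / 1,461 = 0.82%.

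**Irregular attendance (assumed).** Let each visit from month 3 vary independently around its target with standard deviation s. A gap then has mean m = 91.3125 − 91 = 0.3125 above the cut-off and standard deviation σ = s√2. The expected loss per gap is σφ(m/σ) + mΦ(m/σ). For s = 7, σ = 9.90 and the loss is 3.95 + 0.16 = 4.11 days; × 15 = 62 days. Simulation gave:

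| Assumed s (days) | Days removed | Share of 1,461 |
|---|---|---|
| 3 | 27.8 | 1.9% |
| 7 | 61.8 | 4.2% |
| 10 | 87.4 | 6.0% |
| 14 | 122.1 | 8.4% |

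About half of all gaps (48% to 50%) exceed 91 days in each row, but SAP 4 plans no table of interruption counts.

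**Lateness and gap are different things.** The rule uses the interval between doses. Two successive visits each 5 days late are as far apart as two on-time visits, and cost no more. Exposure is lost when the interval lengthens.

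**A missed dose remains visible.** Removing the month 24 dose leaves a gap from day 639 to day 822, which is 183 days, so 183 − 91 = 92 interruption days. Total with exact attendance: 5 − 1 + 92 = 96. With s = 7 the total is 145, of which about 92 come from the missed dose.

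**The alternatives.** With a 119-day threshold and duration still counted from day 91, a 119-day gap loses 0 days and a 120-day gap loses 120 − 91 = 29. The loss without a missed dose would be 0% at s = 3, 0.07% at s = 7, 0.8% at s = 10 and 3.0% at s = 14. With a missed-dose rule it is zero by construction, however late the dose.

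**The case for a change.** The strongest case for a change is that elsewhere the documents treat interruption as doses withheld. Protocol 5.5.5 permits it for patients who cannot tolerate the dosing scheme, and SAP 4 remarks that one interruption may span several planned administrations. On that reading, a one-day deduction caused by calendar rounding is not an interruption. Redefining the term would need one sentence in each document and no new data. The arithmetic behind this stands, and so does the point that the summary should not be read as a record of missed doses.

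The rest does not carry. SAP 4 defines the quantity as time without drug action, so it measures coverage and not attendance. The 91-day limit is used consistently: it ends the double-blind treatment phase and starts the post-treatment phase in SAP 2.3.1, and SAP 6.3.1 justifies it as slightly more than three half-lives. Overlapping coverage after an early visit cannot yield more than one exposed day per calendar day, so the absence of credit is correct for such a measure. The 119-day limit serves a different purpose, the attribution of events after the last injection, and borrowing it here would create a step from 0 to 29 lost days. It would also let up to 119 days count between doses but only 91 after the final one. A missed-dose rule needs a boundary between late and missed, and the protocol, with no visit window and no maximum interval, does not supply one.

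**Conclusion.** A fair choice between two descriptive definitions; no change is needed. From the documents alone, perfect attendance loses nothing to about 0.6% of four-year exposure on average, and 0.82% for the least favourable calendar start date or for a literal day-84 dose on the SAP month length. Larger losses rest on assumed visit scatter, independent between visits, and cannot be sized from the plan.

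The consequence is confined to exposure excluding interruptions in the safety set. The rule is the same in every arm, so it does not favour one dose over another unless visit timing differs by arm. SAP 4 also reports treatment duration and patient-years without the deduction, so a reader can see both. No inference depends on it: the primary analysis follows all patients irrespective of treatment, the on-treatment analysis in SAP 6.3.1 keeps patients in the risk set through interruptions, the adverse event window in SAP 7.3.1 runs to 119 days after the last injection or the end-of-study visit, and the event rates in SAP 7.2 use follow-up time. An analyst labelling the table as 91-day drug coverage would remove the remaining room for misreading, and that needs no amendment.

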#### **5 Concomitant medication**

Prior or concomitant medications will be summarized for the safety set in separate tabulations based on the coding dictionary used. Medications will be presented in order of descending frequencies, by preferred terms and grouped by anatomical main group. Tables will show the overall number and percent of patients receiving at least one drug of a particular preferred term and at least one drug in a particular anatomical main group.

Prior medications and significant non-drug therapies are defined as any medications and significant non-drug therapies taken prior to the start of study drug. Concomitant medications and significant non-drug therapies are defined as those used during the double-blind phase. Concomitant medications that were prohibited as per protocol and given during the conduct of the study as well as significant non-drug therapies will be summarized.

Furthermore, classes of medications to be precisely defined in a separate Excel file that will be stored in the Novartis CREDI system, will be summarized separately. These will include classes such as the following:

- Anti-ischemic agents
  - Beta blockers
  - Cardiac glycosides
  - Intravenous or oral nitrates
  - Calcium channel blockers
- Antithrombotic agents (excluding antithrombotic intravenous and subcutaneous drugs intended for acute setting such as abciximab, eptifibatide, or tirofiban, which are not expected to be used chronically and are consequently less relevant in this population – these will be reported separately in the Clinical Study Report)
  - Acetylsalicylic acid (aspirin)
  - Non-aspirin oral anti-platelet agents
    - P2Y12 inhibitors (like clopidogrel, ticagrelor and prasugrel)
  - Direct Thrombin Inhibitors
  - Other antithrombotic agents (e.g. anticoagulants)
- Renin-Angiotensin-Aldosterone System inhibitors
  - Angiotensin Converting Enzyme (ACE) inhibitors (like ramipril)
  - Angiotensin II Receptor Blockers (ARBs)
  - Direct Renin Inhibitors
- Lipid-lowering agents
  - Statins
    - Atorvastatin
    - Rosuvastatin
    - Simvastatin
    - Other statins and statin combinations
  - Non-statins (like PCSK9 inhibitors, ezetimibe, fibrates, binding resins and nicotinic acid)
- Diuretics
  - Thiazide diuretics
  - Non-thiazide diuretics
- Anti-diabetic medications
  - Insulin

- Oral hypoglycemic agents
  - Thiazolidinediones
  - Metformin and other biguanides
  - Sulfonylureas
  - Alpha glucosidase inhibitors
    - sulfonamides
    - glymidine
  - DPP-4 inhibitors
  - Glinides
  - Other oral hypoglycemic agents (incl. SGLT2 inhibitors)
- GLP-1 analogs
- Aldosterone antagonists
- Proton pump inhibitors
- Treatments for macular degeneration

Additionally, the time course of the total daily dose level of concomitant statins will be reported at baseline and tracked over time. For each patient, the daily dose will be determined as follows:

1. For each patient, the daily dose will be determined by the statin use with start/stop date.
2. The daily dose by visit will be presented for the time course of the total daily dose level.
3. For each patient, the daily dose at each visit will be defined as the median of the daily doses since the last visit.
4. The median of individual patient's dose at each visit will be used as the point estimate for the plot/summary
5. In order to have consistent timings for the visit, the visits will be calculated based on protocol visit scheduling.

For this purpose doses of different statins will be equated according to [Table 5-1](#). Median statin dose level, and patients on each standardized dose level will be summarized over time and displayed graphically, where possible. Patients will be classified according to whether they receive no, low dose, medium dose or high dose statins at baseline and during the study. This will be done separately by time since index MI (including finer categorizations than < versus  $\geq$  6 months post index-MI) and by region. If new statins become available or substantial new information regarding their lipid lowering effects becomes available, this table may have to be updated.

**Table 5-1 Conversion table for statin doses**

Dose intensity of statin		Low			Medium	High		
Standardized statin dose  [mg] (atorvastatin equivalent)	Scaling factor	2.5	5	10	20	40	80	160 

Dose intensity of statin		Low			Medium	High		
Standardized statin dose  [mg] (atorvastatin equivalent)	Scaling factor	2.5	5	10	20	40	80	160 
Atorvastatin (LIPITOR)	× 1		5*	10	20	40	80	160*
Lovastatin (MEVACOR)	/ 4	10	20	40	80			
Pravastatin (PRAVACHOL)	/ 4	10	20	40	80			
Simvastatin (ZOCOR)	/ 2	5	10	20	40	80		
Fluvastatin (LESCOL)	/ 8	20	40	80				
Rosuvastatin (CRESTOR)	× 2		2.5*	5	10	20	40	80*
Pitavastatin / itavastatin (LIVALO)	× 20				1	2	4	
Ezetimibe 10 mg + Simvastatin (VYTORIN, INEGY)	× 2 standardized statin dose				10/10	10/20	10/40	10/80
Any other statin + ezetimibe or resin binders (e.g. colesevelam, cholestyramine, colestipol)	× 4 standardized statin dose							
* off label dosing  All other other drugs containing a statin should be reported for the statin dose only (including the following): Statin + fenofibrate, + clopidogrel, + acetylsalicylic acid, + amlodipine, + ramipril  Efficacy response curves flatten at the maximal equivalence of atorvastatin 160 mg or rosuvastatin 40 mg: further LDL lowering attempts with other lipid lowering drugs do not yield further LDL lowering. I.e. any calculated standardized statin dose > 160 mg will be considered as a standardized statin dose of 160 mg.								

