Glycemic status at baseline	
Normoglycemic, pre-diabetic, diabetic
 
Pre-diabetic is defined by one of the followings
 
 
• HbA1c ≥5.7% & <6.5%
 
• FPG ≥100 & <126 mg/dl
 
• FPG ≥ 126 mg/dl at either Visit 1 or Visit 2 (or any unscheduled visit between, but only occurring on one visit)
 
• HbA1c ≥ 6.5% at either Visit 1 or Visit 2 (or any unscheduled visit between, but only occurring on one visit)
 
 
Diabetic is defined by one of the followings
 
 
• FPG ≥ 126 mg/dl at Visit 1 and Visit 2 (or any unscheduled visit between)
 

Subgroups	Definition
	
 
HbA1c <math>\geq</math> 6.5% at Visit 1 and Visit 2 (or any unscheduled visit between)
 
Combination of FPG <math>\geq</math> 126 mg/dl and HbA1c <math>\geq</math> 6.5% as confirmed at Visit 1 and Visit 2 (or any unscheduled visit between)
 
Medical history of Type I or Type II diabetes mellitus
 
Anti-diabetic medication use
 

Smoking status at baseline	Never, current, former
Baseline hsCRP level	$\leq$ 4, $>$ 4 mg/L
Baseline LDL-C level	$<$ 70 mg/dL, $\geq$ 70 mg/dL; Tertiles of baseline LDL-C (This will be done using the calculated LDL-C unless triglycerides $>$ 400 mg/dL in which case a direct (i.e. measured) LDL-C will be used)
Baseline SBP level	$<$ 130 mmHg, $\geq$ 130 mmHg
Baseline DBP level	$<$ 80 mmHg, $\geq$ 80 mmHg
Baseline statin dose level	No, low, moderate, and high
Baseline aspirin usage/dose	Yes / No
Medical history of gout	Yes / No
Cardiovascular risk factors	
Hypertension	Yes / No
Dyslipidemia	Yes / No
Prior PCI	Yes / No
Prior CABG	Yes / No
Prior TIA/stroke	Yes / No
History of heart failure	Chronic Heart Failure occurrence (yes/no)
eGFR MDRD	$<$ 60, $\geq$ 60 & $<$ 90, $\geq$ 90 mL/min/1.73m 
Time since index MI	$<$ 6 vs. $\geq$ 6 months ; $<$ 12 vs. $\geq$ 12 months
Presence of MI prior to index MI	Yes / No

A set of standard safety subgroups shown in [Table 2.3-2](#) will by default be looked at for selected safety analyses (see [section 7](#)).

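### SAP Table 5-1: the ezetimibe/simvastatin scaling factor gives half the dose shown by its own columns, so 10/10 and 10/20 users fall into two different statin-intensity classes

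*SAP*

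**What the plan says.** SAP section 5 (Concomitant medication) makes Table 5-1 the governing conversion: "For this purpose doses of different statins will be equated according to" that table. Patients are then classed as receiving no, low, medium or high dose statin, at baseline and during the study.

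The table has an intensity header, "Dose intensity of statin", above the standardized doses in atorvastatin-equivalent mg. Low covers 2.5, 5 and 10; Medium is 20; High covers 40, 80 and 160. Each row then gives a scaling factor and the product strengths placed under those columns.

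- The plain simvastatin row ("Simvastatin (ZOCOR)") has the factor / 2.
- The ezetimibe 10 mg plus simvastatin row has the factor × "2 standardized statin dose". Its strengths, "10/10 10/20 10/40 10/80", stand under 20, 40, 80 and 160.
- The next row, for any other statin with ezetimibe or a resin binder, has the factor × "4 standardized statin dose" and no printed strengths.
- A footnote sets a cap: "any calculated standardized statin dose > 160 mg will be considered as a standardized statin dose of 160 mg".

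Table 2.3-1 in SAP section 2.2 lists "Baseline statin dose level" as an efficacy subgroup with four levels.

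**The concern.** The row gives two instructions, a factor and a column position, and they disagree. A programmer who calculates from the factor and one who looks up the column will put the same patient in different intensity classes.

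The classification is used in several places:

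- the statin dose and class summaries over time, by time since index MI and by region (SAP section 5), on which the lipid safety evaluation in SAP 7.4.7 also draws;
- the baseline statin subgroup for MACE and the key secondary variables (SAP section 2.2);
- the covariate list in SAP 6.3.1. For the primary endpoint that adjusted model is optional, but SAP 6.3.2 and 6.3.3 plan analyses with the same covariates for the key secondary cardiovascular endpoint and the other secondary endpoints.

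If the row is not settled beforehand, someone has to choose between the two versions, possibly after the treatment codes are known.

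**Working it through.** All inputs come from SAP Table 5-1.

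**Step 1: are the columns intact?** For each single-statin row, standardized dose = product mg × row factor. All seven rows match their printed columns exactly:

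- atorvastatin (× 1): 5, 10, 20, 40, 80, 160 stay unchanged
- lovastatin and pravastatin (/ 4): 10, 20, 40, 80 give 2.5, 5, 10, 20
- simvastatin (/ 2): 5, 10, 20, 40, 80 give 2.5, 5, 10, 20, 40
- fluvastatin (/ 8): 20, 40, 80 give 2.5, 5, 10
- rosuvastatin (× 2): 2.5, 5, 10, 20, 40, 80 give 5, 10, 20, 40, 80, 160
- pitavastatin (× 20): 1, 2, 4 give 20, 40, 80

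The pitavastatin row is the useful control. Like the combination row it starts with three empty cells, and it still lines up. A column shift from reading the PDF is therefore unlikely.

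**Step 2: the combination row as written.** Standardized simvastatin dose = mg / 2. Applying the stated factor gives (mg / 2) × 2.

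| Strength | Simvastatin standardized | Factor as written | Class | Printed column | Class |
|---|---|---|---|---|---|
| 10/10 | 5 | 10 | Low | 20 | Medium |
| 10/20 | 10 | 20 | Medium | 40 | High |
| 10/40 | 20 | 40 | High | 80 | High |
| 10/80 | 40 | 80 | High | 160 | High |

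The result is half the column value at all four strengths. The class differs at 10/10 and 10/20. The 160 mg cap does not bind under the written factor.

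**Step 3: which factor fits the columns?**

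- 4 × standardized dose: 4 × 5, 4 × 10, 4 × 20, 4 × 40 = 20, 40, 80, 160
- 2 × simvastatin mg: 2 × 10, 2 × 20, 2 × 40, 2 × 80 = 20, 40, 80, 160

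The two are the same rule, and both match the columns.

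**Step 4: consistency with the next row.** Atorvastatin 10 mg and simvastatin 20 mg both standardize to 10 mg. With ezetimibe added, the next row takes atorvastatin to 4 × 10 = 40 mg (High). The combination row as written takes simvastatin to 2 × 10 = 20 mg (Medium). The printed columns put simvastatin 20 mg with ezetimibe at 40 mg, in agreement with the next row.

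**Step 5: who moves in the covariate.** SAP 6.3.1 appears to use three levels: none, low or medium, and high. On that reading 10/10 stays in the pooled middle level, and only 10/20 moves, from the middle level to high.

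**The case against.** The best defence is that the number 2 is right and only its label is wrong. In every single-statin row the factor multiplies the product's own milligrams. Read that way, 2 × simvastatin mg gives every printed column, and the intended classes are not in doubt. This is plausible, but it does not rescue the cell. The words refer to the standardized dose, a term the table header defines. The next row uses the same phrase for a mixture of statins, where it can only mean a multiple of the standardized dose. One phrase cannot carry two meanings in adjacent rows.

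A second defence is that the four strengths are printed, so a programmer can look up the class and ignore the factor. That is true for those strengths. However, the capping footnote speaks of calculated doses, and section 5 works with total daily doses built from start and stop dates, so calculation is clearly expected.

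The points about consequence stand:

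- The number of patients on this combination is not given.
- 10/40 and 10/80 stay High under either rule.
- Table 2.3-1 does not cite Table 5-1, and calls the middle class moderate rather than medium. The link from the conversion table to the subgroup is therefore a natural reading through section 5, not an explicit instruction.
- The subgroup is one of many meant to assess consistency, and the SAP itself warns that spurious imbalances are to be expected.

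**Conclusion.** The concern holds: the row is wrong as written. The stated factor gives 10, 20, 40 and 80 mg where the columns show 20, 40, 80 and 160 mg. Users of 10/10 move between Low and Medium, and users of 10/20 between Medium and High. For 10/40 and 10/80 the standardized milligrams halve but the class does not change.

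The consequence is minor. The primary stratified log-rank test, its strata, the alpha allocation and the power do not use this table. What is affected is the section 5 statin summaries, the covariate (10/20 only, if low and medium are pooled) and, assuming the subgroup follows section 5, the baseline statin subgroup. How far any of these would shift depends on the number of 10/10 and 10/20 users, which the documents do not give.

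**What to change.** Change the factor in the ezetimibe plus simvastatin row of Table 5-1 to 4 times the standardized statin dose or, equivalently, to 2 times the simvastatin dose in mg. Either wording reproduces the printed columns, and the first also matches the row below. If the sponsor did intend the written factor, the four entries should instead move one column to the left, to 10, 20, 40 and 80 mg. One version or the other should be fixed before unblinding.

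In the same edit, have the statin entry in Table 2.3-1 cite Table 5-1 and use the same name for the middle class.

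The cost is one table cell and one cross-reference. No new data are needed, and the primary analysis does not change.
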